SEAS Scientific Exercises Approach to Scoliosis

SOP Standard Operating Procedure

TMG Trial management group

WCTU Warwick Clinical Trials Unit

1 Background

1.1 Epidemiology and burden of condition

Adolescent Idiopathic Scoliosis (AIS) is often referred to as a structural lateral curvature of the spine, although, it is actually a 3 dimensional spinal deformity that results in lateral deviation, rotation and flexion/extension of the vertebrae. It is of unknown cause that occurs at or near the onset of puberty(Lonstein 2006). AIS is commonly diagnosed using the Cobb Angle and to meet the definition the lateral curvature must have a Cobb angle of greater than 10 degrees. A Cobb angle is measured using standing postero-anterior radiographs of the full spine and assesses the lateral curvature of the spine. To do this the most tilted vertebrae above and below the apex of the curve is identified. The angle between intersecting lines drawn perpendicular to the top of the top vertebrae and the bottom of the bottom vertebrae is the Cobb angle (See Figure 1).

[figure not shown]

Figure 1 Measurement of Cobb Angle

The prevalence of AIS in children aged 10-16 years is 1-3% (Parent, Newton and Wenger 2005, Kesling and Reinker 1997), implying 50,000 - 150,000 sufferers in the UK (Office 2009). The effects of AIS include pain, cosmetic concerns, functional limitations, cardiorespiratory problems and possible further curve progression in adulthood (Weinstein et al.

2003). About 10% of AIS cases require surgical or active conservative management (UK 2010). Current UK management includes monitoring, bracing for some and, for the most progressive and serious cases, surgery. Surgery is generally only undertaken when spinal curvature reaches a Cobb angle >45-50 degrees (Weinstein et al. 2008). Surgery is a very extensive procedure, with exposure of large segments of the spine and substantial fixation which, whilst reducing curve progression, also permanently limits mobility in the affected part of the spine. Surgery also comes with a risk of complications estimated to occur in approximately 6% of patients undergoing spinal fusion for scoliosis and include pulmonary complications, wound infection and neurological damage (Coe et al. 2006).

1.2 Existing knowledge

Currently, the main components of conservative management of scoliosis in the UK are bracing and watchful waiting. Braces are an intrusive and uncomfortable intervention. Two recent publications reported bracing protocols that lasted up to four years and required the brace to be worn for 23 hours per day (Wong et al. 2008, Nachemson and Peterson 1995). The effectiveness of bracing protocols is unclear (Negrini et al. 2010). Exercise is a promising intervention for which there is an emerging, although low quality, evidence base (Negrini et al. 2008, Fusco et al. 2011). The rationale is to use exercises that promote spinal re-alignment, and hence to either improve or halt progression of the curvature. Exercise is potentially a low cost intervention and, even if not effective in all, it would be of substantial benefit if the relative risk reduction in progression to curvature of greater than 45 degrees, or requirement for surgery was reduced in a modest proportion of those participating. It is thought that exercise should be applied as early in the disease process as possible.

Exercise therapy is less commonly provided in the UK and USA, although it is routinely used in Europe (Romano et al. 2010). Within Europe, there are various schools of exercise therapy for AIS. The Schroth method (originating in Germany), Scientific Exercises Approach to Scoliosis (SEAS, Italy), and the Dobomed (Poland) are amongst the most well-known and reported in the literature. However, there is little evidence to support the choice of one over another, or to provide evidence of effectiveness.

The rationale for exercise to manage AIS is that a number of underlying impairments in spinal muscular function and postural ability contribute to or accompany the development of curvature, and are potentially reversible. Electromyography (EMG) of trunk muscles in AIS patients indicate disrupted patterns of muscle recruitment under static and dynamic conditions, in a broad range of postures. These asymmetries extend to the paraspinal lumbar and abdominal oblique muscles, and are associated with a disparity in trunk isometric rotation strength between sides (Avikainen, Rezasoltani and Kauhanen 1999, Mooney, Gulick and Pozos 2000, McIntire et al. 2007, McIntire et al. 2008). In keeping with differential muscle activity, there are differences in muscle fibre-type distribution on the convex and the concave side of the curve. AIS patients exhibit greater balance control problems and proprioceptive impairments (Simoneau et al. 2006, Bruyneel et al. 2010). AIS may be associated with distorted body schema resulting in a mismatch between actual body alignment and patients' internal bodily representation of the body (Smania et al. 2008).

Hence to improve function and reduce/stabilise curvature the exercise programmes must include strengthening of all affected muscle groups, exercise to encourage the appropriate magnitude and timing of muscle activation, proprioceptive elements and postural/body awareness components. The programme will require careful tailoring to each individual. There is evidence that such approaches can remediate underlying impairments in EMG activation and strength, although effects may well be limited to curves with a Cobb angle of less than 50 degrees (Weiss 1993, Schmid et al. 2010, Mooney et al. 2000, McIntire et al. 2007, McIntire et al. 2008).

Although there is a theoretical basis for exercise in AIS, there is little robust evidence that there is a significant effect on curve progression. There are relatively few studies investigating this important outcome (Negrini et al. 2008), and only one randomised controlled trial (RCT). Wan et al (Wan, Wang and Bian 2005) recruited 80 participants with double curves (mean age 15 yrs, SD 4; 43 female, 37 male) and randomised them to either a control treatment or a 6 month exercise programme that targeted impairments of strength and neuromuscular activation. All participants received electro-stimulation therapy and postural retraining. Curve progression was halved in the exercise group (15° v 7°, p<0.01) but the quality of the trial was poor. There is no information on cost-effectiveness of the various approaches and whether they offer a viable alternative to surgery and bracing. The exercise approach used in this study differs greatly from the general consensus within Europe where exercises are used routinely as treatment for AIS. A small number of prospective cohort studies have attempted to evaluate the European schools of exercise including SEAS and Schroth (Negrini et al. 2008). Although these studies show a favourable outcome in support of exercises, the research is problematic due to a variety of reasons. These include a lack of control group, failure to randomise, the reporting of very small statistically significant but not necessarily clinically important differences in Cobb angle, poor statistical analysis, limited descriptions of baseline characteristics of participants, adherence to treatment and the exercise programmes evaluated (Mordecai and Dabke 2011). Clear evidence that these approaches are beneficial is currently lacking.

1.3 The need for a pilot trial

A high quality RCT is needed to assess the effectiveness of exercises for patients with AIS. The ultimate aim of this pilot study is, if feasible, to progress to such an RCT which would demonstrate definitively whether or not exercise is clinically and cost effective in AIS management. We estimate that a definitive RCT will require in the region of 400-500 participants (power calculations are in Section 3.7.1). This presents several challenges and is the reason that a pilot study is required before carrying out a full RCT. AIS is a relatively rare condition, and we will require commitment from a substantial proportion of the specialist centres managing AIS in the UK. We need to ensure that there are sufficient numbers of cases who can potentially benefit from the treatment and are willing to participate. The clinicians managing these cases will need to have confidence in the alternative treatments delivered within an RCT to ensure they are willing for patients to be randomised. We also need to maximise the chance that exercise can be effective, not only

by selecting the optimal prescription of exercise, but designing an intervention that encourages compliance. The assumptions underlying the sample size calculation and estimates of recruitment rates also need to be examined.

1.4 Good Clinical Practice

The trial will be conducted in full conformance of the principles of the "Declaration of Helsinki" (1964) (as amended in Tokyo, Venice, Hong Kong, South Africa and Scotland), the Medical Research Council (MRC) Good Clinical Practice Guidelines, and applicable UK legislation.

1.5 CONSORT

[figure not shown]
The study will be reported in line with the CONSORT (*Consolidated Standards of Reporting Trials*) statement (Lancet 2001, **357**: 1191-1194).

2 Trial Design

2.1 Summary of the pilot trial

We plan to randomise 50 participants in the pilot RCT to evaluate an exercise intervention compared to usual care (control arm) for patients with mild to moderate AIS. This pilot trial will test recruitment including willingness to be randomised, acceptability of the intervention, ease of delivery within the NHS, data collection and outcome measures. This will allow the evaluation of the viability of a definitive RCT and to finalise a trial protocol. The exercise intervention and control arm have been developed through a systematic literature review, a survey of current practice and consultation with patients and expert clinicians.

2.2 Flow Diagram

2.3 Aims and Objectives

2.3.1 Aims

The aim is to carry out a pilot RCT to:

- 1) Develop and refine a best evidence intervention, ensuring that it can be delivered within the normal patterns of NHS delivery
- 2) Assess the key parameters needed to finalise the design and project management plan for a definitive multi-centre RCT to evaluate the clinical and cost-effectiveness of scoliosis-specific exercise treatment in AIS in comparison to standard practice.

2.3.2 Objectives

These aims will be achieved through the following objectives:-

- To randomise 50 adolescents to the pilot RCT at three participating hospital trusts.
 The willingness of individuals, their families and surgeons to take part in randomisation needs to be established as this is vital to the success of a future definitive RCT.
- 2) To finalise a main trial protocol, including the choice of outcome measures. The main issues in outcome measures are the need to reduce as much as possible unnecessary exposure to ionising radiation, and to ensure outcomes are responsive to patients' and clinicians' concerns.
- 3) To assess and finalise the training requirements for the intervention delivery in the main trial.

2.4 Eligibility for pilot RCT

2.4.1 Inclusion criteria

- 10-16 years olds with Adolescent Idiopathic Scoliosis (AIS).
- Mild to moderate AIS, defined by a Cobb angle of between 10 50° (measured radiographically).

2.4.2 Exclusion criteria:

- Individuals who have had previous surgery or are on a waiting list for spinal surgery within the next 6 months.
- Individuals with non-idiopathic scoliosis, for example congenital malformations, syringomyelia, neurofibromatosis, spina bifida, polio and cerebral palsy.

[figure not shown]
Other treatments including bracing and previous physiotherapy are not exclusion criteria.

2.5 Informed Consent

We will follow the MRC guidance on seeking consent from children to participate in research (MRC 2004). Where a child is assessed as competent to consent to take part in the study, we will seek his or her consent. In addition, we will seek agreement from parents to allow their children to participate. Where a child is judged not to have capacity to consent to participate, consent will be obtained from his or her parent or guardian and agreement will also be sought from the child. Thus in all cases we will have agreement from both the child and the parent. Researchers responsible for obtaining consent will have training in seeking consent from children and assessing capacity to consent (from [name] and a Paediatrician with research expertise). We will take care to provide information that is age appropriate and information sheets will be developed with input from a child with the condition and a parent. Participants will be reminded at regular and pertinent intervals that consent is voluntary and can be withdrawn at any stage.

The initial approach will be made by a member of the clinical team responsible for the care of the child (See Figure 2 for flowchart describing a participant journey through the study). A verbal explanation of the study will be provided either by a member of the clinical team, Comprehensive Local Research Network (CLRN) or locally employed research staff, depending on the context of each site. The research team will only be provided with details of those families that have provided verbal consent to be approached and have their details shared. The research team will contact the family and if they are interesting in taking part then a research clinic appointment will be arranged at the same hospital they attended for their scoliosis management. They will have at least 24 hours to consider their involvement before attending for this appointment. The research clinic will be run by a research clinician (either a nurse or physiotherapist employed by Warwick Clinical Trials Unit (WCTU) or the CLRN). At the research clinic appointment, informed consent will be obtained from the child and parent (carer) following discussions and any questions having been answered.

Figure 2 Participant Journey through the study

Attend physiotherapy department

Informed of treatment allocation

Physiotherapist sends a letter to the GP informing them that their patient is taking part in the study and their treatment allocation.

Exercise intervention (n=25)

- 6-9 sessions
- home exercise programme over 6 months

Standard Care (n=25)

1 session

On completion of the exercise intervention families will be invited by their physiotherapist to take part in an interview

- Families will be invited until 5-6 families are interviewed
- If they wish to do so then their contact details will be given to the lead qualitative researcher and the family are provided with a Qualitative study PIS.

Telephone call

Lead qualitative researcher contacts the family.

- Further explanation of interview study is provided.
 - The family asks questions.
- Appointment arranged to carry out interviews if the family are happy to do so at least 24 hours later.

Interview appointment

The family meet with the lead qualitative researcher.

- Discuss the interview study PIS.
 - The family ask questions.
- Consent is taken if the family are happy to proceed.
 - Both the child and their parent are interviewed.

The family is contacted by the study team to arrange 6 month follow up appointment.

Follow up research clinic appointment

- Consent to collect data is reconfirmed
- Child undergoes physical assessment
- Child and parent(carer) complete a questionnaire

2.6 Planned investigations

2.6.1 Evaluation of an exercise intervention compared to usual care

2.6.1.1 Development of the interventions

A period of intervention development has been undertaken. This has included carrying out a survey to establish current usual practice to inform the content of the control arm. A review of the current evidence base was carried out including the updating of the most recent available systematic literature review (Romano et al. 2010). Fifteen clinicians experienced in the management of AIS attended an intervention development day in April 2012. We have utilized their knowledge and experience to refine the intervention, establish training needs and ensure its acceptability to the clinical community. User groups and participants will also be consulted on the suitability of the intervention, outcome measures and trial materials.

2.6.1.2 The exercise intervention

Aims of the exercise intervention

The aims of the exercise intervention are based on the European guidelines for the management of AIS (Negrini et al. 2012, Weiss et al. 2008). Broadly, the aims are to provide a treatment to avoid surgery and or bracing. The specific aims of the exercise intervention are:

- 1) Achieve active auto-correction of spinal deformity
- 2) Address restricted range of movement that may prevent active auto-correction
- 3) Achieve maintenance of the auto-corrected position during movement including integration in activities of daily living
- 4) Improve sensorimotor integration and balance reactions while maintaining the corrected position
- 5) Provide education and support for the participant and family
- 6) Promote strategies to encourage adherence to the exercise programme

Delivery of the exercise intervention

Participants will be asked to carry out the exercise programme primarily as a daily home exercise programme with initial physiotherapy assessment and regular therapy review sessions (up to a maximum of 9 sessions over the 6 months) to provide support, encourage adherence, and allow monitoring and progression of the exercises. Although some clinicians, particularly those following the European schools of thought, advocate prolonged in-patient exercise programmes, recent evidence suggests that such intensive programmes that disrupt normal schooling and socialisation are not necessary (Weiss and Goodall 2009).

Content of the exercise intervention

Each participant will be assessed by their physiotherapist and given an individualised exercise programme based on the presenting spinal deformity. The first step of the exercise programme is to teach the participant to correct their posture (auto-correction to reduce the spinal deformity). Visual, tactile and verbal feedback will facilitate this. Once this has been achieved the participants will be given additional exercises that progressively challenge their ability to maintain the corrected posture by altering position, adding load or resistance, adding movement or distractions and incorporation into activities of daily living.

Physiotherapists will be provided with a manual containing a library of exercises that address the aims of the exercise programme from which they can select the appropriate exercises for each participant. The participant will be given a small number of exercises at any one time which will be replaced by exercises of increasing difficulty as mastery of each exercise is achieved. Participants will carry out up to 30 minutes of exercises each day.

Adherence with the exercise programme will be vital to its success. Many of the approaches in Europe provide extensive supervised sessions. However, this is not feasible for the NHS to provide supervision for the duration and frequency reported in the literature (e.g 5 days a week for 4 weeks (Rigo et al. 2008)). Instead we will utilise behavioural methods and techniques including exercise contracts, an on-line exercise diaries and on-line chat forum moderated by the physiotherapists at each centre to promote adherence (Sheeran, Trafimow and Armitage 2003).

The on-line resources will be designed so that they can be hosted by NHS.net, are compliant with NHS security standards and can be disseminated readily into the NHS. They will provide physiotherapists and participants with a structured approach to prescribing/progressing the physical and behavioural elements of the exercise programme, and a diary for participants to record their progress and concerns (including any adverse events). It will only be accessible to the treating therapist, individual participants (and their parents depending on the age of the child) and research team. Each participant will be provided with a unique user name and password to ensure that all information is confidential and protected. We are confident that all children will have access to computers – the vast majority through home provision (Harris 1999) or school or library alternatives. We will check computer access carefully as the study progresses and will provide alternative materials available if this is difficult and likely to be a barrier. The behavioural strategies,

which are not monetary in nature, have been successful in other areas of health intervention for adolescents. Exercise diaries are effective in improving adherence to home exercise programmes, particularly if the participant is aware that the diary is being monitored by a health professional (Moseley 2006). The diary will form a useful point of discussion in the consultations between participants and physiotherapists. As well as recording number of sessions attended, we will also ask therapists to make an assessment of the participants' adherence.

Alongside the exercise programme and adherence strategies, the physiotherapist will also provide education and support for the participant and family. This will include discussions about the participant's expectations of the exercise programme, education about AIS including participation in sporting activities and address any concerns or worries (e.g. concerns about the exercises, concerns about body image) of the participant and/or parents.

Physiotherapist training

The physiotherapists delivering the exercise intervention will receive between one and two day's training with follow-up support from the research team. From the information collected at the intervention development day, we anticipate that the majority of clinical skills for exercise prescription already exist but some specific training about exercise prescription in patients with AIS will be included. A health psychologist ([name]) will provide training on the use of the adherence strategies, managing psychosocial issues related to children and the on-line forum. Training in trial procedures will ensure that the physiotherapists have an understanding of the need to comply with the trial protocols and governance procedures. The physiotherapists will also be trained in delivering the control intervention. The interventions will be documented in a manual, along with training materials and a theoretical justification for the various components. Support will be provided by the research team based at WCTU and two physiotherapists who have specialized in AIS and are collaborators on the trial ([name] and [name]).

2.6.1.3 The control intervention

Participants randomised to the control arm will receive 1-2 sessions (up to one hour) with a physiotherapist which will encompass musculo-skeletal assessment, information and advice regarding their condition and support groups (e.g. SAUK), and, if relevant, information about brace use and care. Participants in both arms will continue to attend for orthopaedic review as per standard practice at their centre. The control intervention will be delivered by the same physiotherapists who deliver the exercise intervention.

2.6.2 Qualitative study

We will also conduct a qualitative study alongside the pilot RCT. Participants, their parents and the physiotherapists delivering the intervention will be interviewed. Our aim is to explore factors that influence the acceptability of the trial and interventions, issues influencing exercise adherence, and appropriateness of the chosen outcome measurement to participants. Further details are provided in a separate protocol.

2.7 Outcome Measures

2.7.1 Criteria for progression to a randomised controlled trial

The primary outcome of this feasibility trial is to assess if the criteria for progression to a full RCT has been achieved. The progression criteria will be:

1. To demonstrate that the assumptions underlying the sample size, in particular the rates of progression are as anticipated in three centres, that variances are within our estimated range, and that we can achieve or better the recruitment target in these three centres.

We estimate the definitive trial will include between 300-400 participants. This would allow detection of a standardised difference of 0.3, equating to a clinically important 6 degree difference between groups in the Cobb angle (Negrini et al. 2010) (SD of 15 degrees using 80% power, alpha <.05, loss to follow-up of 30%), and also a relative risk reduction of 1.4 in the numbers proceeding to surgery, assuming that 20% of the control group progress to surgery.

2. That we have sufficient numbers of centres, with sufficient numbers of participants in order to finalise the recruitment strategy for a main trial.

Thirty-five NHS Trusts managing AIS in the UK have been identified that could potentially recruit participants in the main trial. There is a wide range of permutations of time, rate of recruitment and number of centres recruiting that could achieve the anticipated sample size but the optimal strategy needs to be finalised. We will also be able to confirm whether patients and their families are willing to accept randomisation as opposed to sourcing exercises themselves, and whether our estimates of the numbers potentially eligible, meeting the various inclusion and exclusion criteria, and finally being randomised are accurate.

3. To have developed an intervention which, based on theoretical models, has sufficient therapeutic dose to limit or reverse progression of curvature and has maximal chance of engaging adherence in adolescents. We must demonstrate that we can deliver a theoretically sufficient dose within current and reasonable levels of NHS resourcing, and that greater than 60% of adolescents will have attended all

supervised sessions and provide evidence that they are undertaking exercises at home.

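### Section 2.7.1 equates a standardised difference of 0.3 with 6 degrees at SD 15, but 6/15 is 0.4; the stated 300-400 does not give 80% power for 0.3, and section 1.3 gives 400-500

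*Protocol*

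**What the plan says.** Section 2.7.1, under the first progression criterion, gives the size of the future trial: "We estimate the definitive trial will include between 300-400 participants". It then states what that size achieves: "This would allow detection of a standardised difference of 0.3, equating to a clinically important 6 degree difference between groups in the Cobb angle". The inputs follow in brackets: "SD of 15 degrees using 80% power, alpha <.05, loss to follow-up of 30" per cent. The same sentence says the size also serves a comparison of the numbers going on to surgery, assuming 20% in the control group.

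Section 1.3 describes the same trial differently: "We estimate that a definitive RCT will require in the region of 400-500 participants". For the power calculations it refers to Section 3.7.1. Section 3 of the protocol contains only 3.1, and the calculation stands in 2.7.1. Section 7.4 has the same kind of slip (3.7.2.1 where 2.7.2.1 is meant), which suggests a renumbering that was not carried through.

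Criterion 1 asks whether the assumptions behind the sample size hold, including the variances, and whether the three pilot centres reach their recruitment target. Criterion 2 asks whether there are enough centres and participants to plan recruitment to the anticipated main-trial size. Sections 2.8 and 6.1 say that the target effect size and the final sample size will be settled after the pilot.

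**The concern.** A standardised difference is the raw difference divided by the SD, so any two of the three figures fix the third. Here all three are given and they do not fit. The reader cannot tell whether the planning target is 6 degrees or 0.3 SD units, and the two need very different trials. The two stated size ranges meet only at 400, so they do not settle the matter.

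This matters because section 2.7.1 makes the progression criteria the primary outcome of the pilot. Whoever applies criterion 2 needs to know roughly how large a trial the available centres must supply. A planner who took 0.3 as the target and 300-400 as its size would expect 80% power and have much less.

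**Working it through.** **Inputs from section 2.7.1:** difference 6 degrees, SD 15, standardised difference (d) 0.3, power 80%, alpha .05, loss 30%, total 300-400. **From section 1.3:** total 400-500. **Assumed, because not stated for the main trial:** two-sided test, 1:1 allocation, loss applied as N/(1 - 0.30).

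**Step 1, the ratio.**
- 6/15 = 0.40, not 0.3.
- 0.3 x 15 = 4.5 degrees.
- 6/0.3 = 20, so 6 degrees and 0.3 agree only at an SD of 20, which the protocol does not mention.

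Sidedness, allocation and attrition do not enter this step.

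**Step 2, the size each value needs.** Normal approximation per arm: n = 2(1.960 + 0.842)²/d² = 15.70/d².
- d = 0.3: 15.70/0.09 = 174.4, so 175 per arm. The t-test calculation gives 176 per arm, 352 evaluable, and 352/0.7 = 503 randomised.
- d = 0.4: 15.70/0.16 = 98.1, so 99 per arm. The t-test calculation gives 100 per arm, 200 evaluable, and 200/0.7 = 286 randomised.

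The plan's 300-400 is therefore not reproduced as a randomised total from either value: 286 lies below it and 503 above it. Section 1.3's 400-500 is just about reached by 0.3, at its upper end.

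**Step 3, the power the stated sizes give after 30% loss.** Evaluable per arm = 0.7N/2.

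| Randomised | Evaluable per arm | Power, d = 0.3 | Power, d = 0.4 | Difference detectable with 80% power at SD 15 |
|---|---|---|---|---|
| 300 | 105 | 58% | 82% | 5.8 degrees |
| 400 | 140 | 71% | 92% | 5.0 degrees |
| 500 | 175 | 80% | 96% | 4.5 degrees |

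**Step 4, other conventions for d = 0.3.**
- One-sided 5%: 276 evaluable, 276/0.7 = 395 randomised, inside 300-400.
- Loss added as N x 1.3: 350 x 1.3 = 455, inside 400-500.
- Before attrition: about 350, inside 300-400.
- Baseline adjustment with an assumed correlation of 0.5 to 0.6: 375 down to 320 randomised.

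Each could explain one of the ranges. The protocol states none of them, and none changes step 1.

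**The case against.** The best defence is that the plan is sound in natural units. Six degrees is the difference it calls clinically important, SD 15 is explicit, and 300-400 randomised gives 82-92% power for that. On this view 0.3 is a wrong label and section 1.3 is out of step. That stands as far as it goes: the stated size does serve the 6-degree target. It does not make the sentence right, because the sentence claims 0.3 and the size does not deliver it.

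A second defence is that 0.3 explains both ranges, with about 350 evaluable falling in 300-400 and about 503 randomised at the top of 400-500. This may be how the figures arose. But section 2.7.1 says the trial will include 300-400 and lists the 30% loss among the inputs, so as written that range already allows for attrition. The one-sided reading, at 395, likewise needs a convention that the protocol does not state.

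A reader might go further and infer that criteria 1 and 2 are both judged against a wrong target. The documents do not support that. The recruitment target in criterion 1 concerns the three pilot centres and is the pilot's own 50. Its variance check has an explicit SD of 15; the SD of 20 appears only by back-calculation from 0.3. Criterion 2 sets no numerical pass mark, and sections 2.8 and 6.1 say the final size will be re-derived.

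A reader might also infer that the definitive trial is bound to be underpowered. That follows only if 0.3 is the true target.

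**Conclusion.** The point holds as an internal contradiction in the planning figures. Six degrees at SD 15 is a standardised difference of 0.40. The stated 300-400 does not give 80% power for the stated 0.3, and sections 1.3 and 2.7.1 give different sizes for one trial. The main-trial size that criterion 2 relies on is undetermined, between about 286 and 503 randomised, a factor of about 1.8 (503/286). The step 1 result needs no assumption; the sizes and powers rest on a two-sided 5% test, equal allocation and 30% loss.

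The consequence is limited. The size is provisional, and the pilot's sample of 50, which section 2.8 bases on estimating variance and recruitment rates, does not depend on it.

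**What to change.** State one consistent set in section 2.7.1: raw difference, SD, standardised difference, sidedness, power and loss. Say whether each total is before or after attrition. Two consistent versions, under the assumptions above, are:

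- If 6 degrees and SD 15 stand: *standardised difference 0.4, about 286 randomised with 30% loss; 300-400 randomised gives 82-92% power.*
- If 0.3 is intended: *4.5 degrees at SD 15, about 503 randomised with 30% loss*, with the 300-400 replaced.

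Then align the range in section 1.3 with the chosen version and correct its cross-reference to 2.7.1. Check the chosen size separately against the surgery endpoint in the same sentence, since the Cobb-angle calculation does not cover it.

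The cost is a change of wording in two sections, with no change to the pilot's conduct or sample size. It should be made before the progression criteria are applied.
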